## 4. DEVICES, SOFTWARE AND PROCEDURES

### 4.1 MFAM Workstation

The mFAM Workstation operates in direct interface with the CARTO® 3 System V7 workstation. Coordination between the Workstation and the CARTO® 3 System includes:

- Automatic import of data recordings (such as position, respiration, and force) from the CARTO® 3 System
- Analysis of data by proprietary software algorithms
- Transfer of the 3D anatomical structure to the CARTO® 3 System
- Display of the 3D anatomical structure on the monitor of the CARTO® 3 System
- The maps can be superimposed over original 3D maps and the real-time position of the mapping catheter in the CARTO® 3 System.

[figure not shown]

Figure 5: Real time data is acquired by placing the catheter into pulmonary veins and is transferred to the mFAM workstation, where it is processed, and the image maps are transferred back to the CARTO workstation.

#### 4.2 Ablation catheters:

The AF ablation procedure will be performed using any of the following marketed catheters:  
 (Note: the ablation catheters listed below are FDA approved for the treatment of paroxysmal atrial fibrillation but not persistent.)

- Biosense ThermoCool SmartTouch SurroundFlow (STSF) ablation catheter
- Biosense ThermoCool SmartTouch (ST) ablation catheter

## 5 SCHEDULE OF TREATMENT AND TESTS

TABLE 1: SCHEDULE OF TREATMENTS AND TESTS:

	Baseline	Procedure	Discharge
Type of visit	Office	Hospital	
Informed Consent	X		
Brief History & Physical	X		
CT or MRI	X		
Echo	X		
EKG	X		
Medications	X	X	X
Adverse Events		X	X

## 6 ENDPOINTS

### PRIMARY CLINICAL ENDPOINTS

1. Accuracy of map (defined as the distance between the ablation points and the surface of the mFAM geometry)
2. Left atrial geometry creation time
3. Fluoroscopy time

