Endpoints:	1. Accuracy of map (defined as the distance between the acquired points and the surface of the left atrial geometry) 2. Left atrial geometry creation time 3. Total Fluoroscopy time (for sites that use fluoroscopy)
Follow-Up	Until hospital discharge
Study Sponser:	[name] , M.D. Icahn School of Medicine at Mount Sinai [name]
Site, Monitoring, and Data Management Center	Electrophysiology Clinical Research Group Icahn School of Medicine at Mount Sinai [name]

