## 2 STUDY OBJECTIVE

This prospective, multicenter observational study will examine the ability of model based fast anatomical mapping (mFAM) with additional software modifications to create left atrial (LA) geometry and guide atrial fibrillation ablation.

Specifically, the study will assess the following issues in atrial fibrillation ablation:

- 1) The accuracy of left atrial anatomy reconstruction, defined as the distance between the acquired points and the surface of the left atrial geometry.
- 2) Left atrial geometry creation time
- 3) Fluoroscopy time for left atrial anatomy creation, for those sites which use fluoroscopy

[figure not shown]
We hypothesize that this approach will lead to accurate LA geometry creation for AF ablation more rapidly than standard techniques without a significant increase in fluoroscopy time.

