## 3 INTRODUCTION, RATIONALE AND BACKGROUND

Atrial fibrillation (AF) ablation for paroxysmal and persistent atrial fibrillation typically involves pulmonary vein isolation (PVI) with left atrial endocardial ablation. With a radiofrequency (RF) ablation approach, the left atrial geometry can be defined using electroanatomical mapping systems.

Reconstruction of left atrial geometry using the CARTO3 system (Biosense Webster, Diamond Bar, CA) is currently performed using a multielectrode mapping catheter that is localized in 3D space utilizing magnetic- and impedance-based technologies with a functionality called FAM (fast anatomical mapping). An alternative approach to creation of left atrial geometry using a novel technique based on a library of previously defined left atrial archetypes – called “mFAM” – has been studied in this investigator-initiated FDA IDE protocol..

[figure not shown]
mFAM applies a model based approach for reconstruction of left atrial chamber anatomy. The model created by fitting a parametric shape model to the point cloud acquired by a catheter. The model includes a geometrical primitive for each of the pulmonary veins, the left atrial appendage, the left atrial chamber, and the mitral valve (as seen in Figure 1-A). The geometrical primitives are blended to form the left atrial structure (as seen Figure 1-B).

*Figure 1: A: Model components. B: Blended model, superimposed on all catheter points' samples (blue), and locations where the catheter was in contact with the surface (yellow).*

A set of more than 200 atrial CT scans were used to initially develop and train this model and define relevant proportions and sizes for “realistic” and anatomically accurate left atria. Examples of these features are: the angle between the PVs, distances from atria center to the mitral valve and pulmonary vein ostia, and the ratio of these values to left atrial volume. This approach provides a way to represent the most probable left atrial geometry with limited information.

This anatomy could be adapted to more accurately represent clinically important points. For points of importance, such as ablation sites, the model deforms to align with the location when there is contact while keeping proportion and sizes congruent with the existing defined anatomical information (as seen in Figure 2).

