*Figure 2: A: Model with original catheter points (gray dots), left side ablation points (blue spheres), first right side ablation point (yellow sphere). B: Adaptation of the model to first right side ablation point. C: Final model, adapted to right side ablation points.*

This model-based fast anatomical mapping strategy has proven feasible in retrospective analyses, and the anatomy has been validated in a pilot study of 21 patients with anatomy in the left atrium collected with a force-sensing catheter. Distance between the mFAM generated anatomy and the reference anatomy was further improved when Navistar data was added to it (see Figure 3). In the current trial, mFAM has been used prospectively to reconstruct left atrial geometry reconstruction for AF ablation procedures..

[figure not shown]

Figure 3: Validation results on a pilot study of 21 patients using a Lasso/Pentaray alone or with Navistar data with 5-10 grams of force. With addition of the Navistar data, distance to reconstruction < 2mm.

In this protocol amendment, we propose expanding enrollment in this multi-center, non-randomized study to evaluate additional improvements on this software solution to guide AF ablation.

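### The primary accuracy endpoint has two conflicting definitions and no stated map state; one version is at least partly a measure of fit, and the other may be

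*Combined protocol and SAP*

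**What the plan says.** Section 6, the only section headed as primary clinical endpoints, lists first: "Accuracy of map (defined as the distance between the ablation points and the surface of the mFAM geometry". The Endpoints row of the Protocol Summary reads: "Accuracy of map (defined as the distance between the acquired points and the surface of the left atrial geometry". Section 2 agrees with the Summary; there accuracy of reconstruction is "defined as the distance between the acquired points and the surface of the left atrial geometry".

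Section 3 describes how the surface is built: "The model created by fitting a parametric shape model to the point cloud acquired by a catheter". The software overview in the same section again describes a shape model fitted to catheter data. Two other sources also shape the surface. One is prior imaging: "A set of more than 200 atrial CT scans were used to initially develop and train this model". The other, where SoundFAM is used, is intracardiac ultrasound frames.

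Section 3 also says that the surface can move after it is built: "For points of importance, such as ablation sites, the model deforms to align with the location when there is contact". The Figure 2 caption illustrates this with "Adaptation of the model to first right side ablation point", followed by a final adapted model.

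Section 17 gives a mean and standard deviation for continuous variables and does not mention the accuracy endpoint. Section 13.4 assigns the statistical analyses to the coordinating center.

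**The concern.** Accuracy is the first-listed objective and the first-listed endpoint. The plan has no accuracy threshold and no test, so the descriptive distance is itself the result. The analyst has two definitions and no rule for choosing between them, and neither definition says which state of the map is scored.

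The choice matters because a distance from a surface to the points that shaped it tends to be smaller than a distance to points that played no part. If acquired points are scored, or ablation points on a surface already moved towards them, the result would tend to flatter the software. If the choice is left until data are in hand, the figure cannot be interpreted with confidence or compared between sites.

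**Working it through.** The plan offers no calculated figure to reproduce: Section 8 says the number of patients (up to 150) was set by feasibility and not by statistical means. The check is a comparison of texts.

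**Step 1. Do the definitions agree?**

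| Place | Points scored | Map state |
|---|---|---|
| Protocol Summary, Endpoints | acquired points | not stated |
| Section 2 | acquired points | not stated |
| Section 6 | ablation points | not stated |

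They do not agree, and all three are current text.

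**Step 2. Could the two point sets be the same?** Acquired points are not defined. The Figure 1 caption separates all catheter samples from "locations where the catheter was in contact with the surface (yellow", so even within the mapping data there is more than one candidate set. The acquired and ablation sets may overlap. Overlap does not remove the conflict: an average over all acquired points and an average over a subset of them can differ.

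**Step 3. Is the acquired-point distance in-sample?** The surface is fitted to catheter-acquired points, so those points are model inputs and their distances are at least partly residuals. How far is unknown, for two reasons. The CT-trained shape and, with SoundFAM, the ultrasound frames also constrain the surface. The documents also do not say whether any acquired points are held out of the fit.

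**Step 4. Is the ablation-point distance in-sample?** That depends on when it is scored. On a map saved before the surface has adapted to a point, that point did not shape the surface by the ablation-site adaptation that Section 3 describes. On a map that has deformed to the point, it did. Since no section states the map state, the ablation-point version may be in-sample.

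**Step 5. Does anything else settle it?** Section 17 does not. Figure 4 reports distances under the labels contact points and magnets, and neither label appears in either endpoint definition. Section 10.3 allows a new map after repeat esophageal deviation, if needed, without saying which map is scored. Section 11 lets the operator revert to non-study software, without saying what is then scored.

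**Step 6. How large is the effect?** An estimate would need distances for the same cases under both point sets, or before and after adaptation. The documents give neither.

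**The case against.** The strongest reply is that this is a feasibility study with a descriptive analysis, no success threshold and two other listed endpoints. On that view the plan needs one consistent wording, and the in-sample argument is plausible but unquantified. It is right that no power or error rate is at stake and that no size can be given. The contradiction still stands, because it sits in the endpoint that a preliminary assessment of performance relies on.

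A second reply is that adaptation is described as something that could happen, when there is contact, and that Section 10.3 does not say maps are adapted during study ablations. This stands, and it is why the ablation-point version is said only to be possibly in-sample.

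A third reply is that ablation points cover only the ablated regions, whereas the aim is reconstruction of the whole left atrium. This also stands, and it is a reason to keep the acquired-point distance as a secondary measure.

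A reader might infer more than the documents support:

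- **That the definitions name two different surfaces.** Section 2 studies the ability of mFAM to create left atrial geometry, and Section 10.3 says mFAM software is used to create it. On an ordinary reading the surface is the same. The terms part only if the operator reverts to non-study software, and how often that happens is not given.
- **That the 21-patient pilot shows optimism.** It compared the mFAM anatomy with a reference anatomy, which is a different measure. Improvement after adding Navistar data does not separate real gain from fit.
- **That Figure 4 gives the size of the bias.** For the 50 IDE cases the mean distance is 1.5 for contact points and 0.8 for magnets, but neither label can be matched to acquired or ablation points.
- **That most of the possible readings can be counted as in-sample.** The point sets may overlap, so they do not form clean categories to count.

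**Conclusion.** Wrong as written: the primary accuracy endpoint has conflicting definitions, and nothing in the document says which governs. The acquired-point version is at least partly an in-sample fit measure. The ablation-point version may be one too, if it is scored on an adapted map.

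The contradiction is certain from the text. The direction of any bias, towards a smaller and more favourable distance, rests on the protocol's own description of fitting and adaptation and on the assumption that the scored points took part in one or the other. The size cannot be determined. The consequence is an ambiguous and possibly optimistic descriptive figure. It would be going too far to say that the reported accuracy is known to be inflated, or that the study's sample size is affected.

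**What to change.** Use the Section 6 ablation-point definition in the Protocol Summary, Section 2 and Section 6, and add the scoring rule to Section 17. Suitable wording for newly enrolled patients: accuracy is the distance from each ablation point to the mFAM map saved before ablation of the region concerned; where a second map is created under Section 10.3, the saved map that preceded those ablation points is used; distances are summarised within each patient and then across patients.

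Report two secondary measures, each labelled as fit to points that were used: the acquired-point distance, with acquired points defined, and the ablation-point distance on the adapted map. Also report how many patients and how many ablation points have no scorable mFAM map because the operator reverted to non-study software. If these were left out without a count, cases in which the map did poorly could go unseen.

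Costs and limits:

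- The wording changes are small, but map versions must be saved during the procedure.
- The primary figure may look less favourable.
- It covers only ablated regions; the secondary acquired-point distance covers the rest.
- Later points may be scored on a map that the operator has since updated.
- Figure 4 already lists 50 IDE cases. If they count towards the total of up to 150, at most 150 − 50 = 100 patients remain for this scoring; if they do not, up to 150. The documents do not say which.

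The change concerns scoring and reporting only and alters no part of patient care.

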## 7 STUDY SUBJECTS

### 7.1 INCLUSION CRITERIA

1. Age  $\geq$  18 years
2. Have either paroxysmal, persistent, or longstanding persistent AF, which are defined as follows:
  - a) Paroxysmal AF – episodes of AF lasting  $<$  7 days and terminate without electrical or pharmacologic cardioversion
  - b) Persistent AF – episodes of sustained AF  $>$  7 days, or episodes of AF which are terminated by electrical or pharmacologic cardioversion after  $\geq$  48 hours.
  - c) Longstanding persistent AF – episodes of AF lasting longer than one year.
3. Planned to undergo first catheter ablation procedure (prior ablation for typical atrial flutter or supraventricular tachycardia is allowed)
4. Ability to understand the requirements of the study and sign the informed consent form.
5. Willingness to adhere to study restrictions and comply with all post-procedural follow-up requirements

### 7.2 EXCLUSION CRITERIA

1. Rheumatic heart disease
2. Current intra-cardiac thrombus
3. Class IV HF
4. Unable to sign consent
5. Unstable angina
6. Recent cerebral ischemic events
7. Contradiction to anticoagulation
8. Recent cardiac surgery (CABG or valve replacement within 6 months)
9. Complex congenital heart disease

## 8 SAMPLE SIZE

This safety and efficacy study will enroll up to 150 patients across 4 US centers. This number has been determined on the basis of study feasibility and not by statistical means. This is a feasibility study of the study software in which the sample size of the clinical investigation is intended to provide preliminary assessment of safety and performance.

[figure not shown]

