14.2. INSTITUTIONAL REVIEW BOARD (IRB) / ETHICS COMMITTEE (EC) INFORMATION

15. CLINICAL CENTERS

16. DATA HANDLING

17. DATA ANALYSIS

## PROTOCOL SUMMARY

Title:	Advanced Model Based Fast Anatomical Mapping Software for Atrial Fibrillation Ablation (mFAM-2)
Objective:	This prospective, multicenter observational study will examine: 1) The accuracy of left atrial anatomy reconstruction using updated mFAM software 2) The left atrial geometry creation time 3) Fluoroscopy time for left atrial anatomy creation
Design:	This is a prospective, multi-center, non-randomized observational trial. The total enrollment will be up to 150 patients.

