## 13 STUDY MANAGEMENT

### 13.1 STUDY DATA COLLECTION AND PROCESSING

The Case Report Form (CRF) is an integral part of the study and subsequent reports. The CRF must be used to capture all study data recorded in the patient's medical record. The CRF must be kept current to reflect patient status during the course of the study. Patients will be identified by a 5-digit number and their initials. The investigator must keep a separate log of patient names and medical record numbers (or other personal identifiers) for their own reference. All study-related documents (CRFs, source medical records, regulatory binder) must be kept in a secure, locked environment with access limited to study personnel only.

The PI is responsible for ensuring the following: 1) adherence to the protocol; 2) verifying adherence to local regulations on the conduct of clinical research; and 3) ensuring completeness, accuracy, and consistency of the data entered in the CRF.

Final CRFs in human readable format must be reviewed and verified for accuracy by the study site Principal Investigator and signed-off. A copy of the final CRF will remain at the investigator's site at the completion of the study.

The CRF numbering convention is as follows:

\_01\_ - \_2\_ - \_3\_ - \_4\_ - A -B -A

\_01\_: Site # must be 2 digits (use leading zero) --- (sites 01-2)

\_2\_ - \_3\_ - \_4\_: patient screening/enrollment # (001 – 050)—must be 3 digits

A-B-A: Patient initials (if no middle initial, use dash)

Total 5 digits and initials for enrolled patients.

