## **15 CLINICAL CENTERS**

The study will be conducted in up to 4 sites in the United States. Each clinical center will be required to obtain IRB/EC approval for the protocol and consent (and their revisions) in a timely fashion, to recruit patients, to collect data and enter it accurately in the electronic data capture (EDC) system, to faithfully follow the protocol and adhere to the standards of Good Clinical Practice (GCP). In addition, centers will be required to provide the DCC with the information necessary for interim, annual, and final reports, to provide source documents, data and regulatory documents for study monitors, provide prompt responses to DCC inquiries, and to participate in analyses and reporting of study results.

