## **16 DATA HANDLING**

Information about patients will be kept confidential and managed according to the requirements of the United States of American Health Insurance Portability and Accountability Act of 1996 (HIPAA). Those regulations require a signed patient authorization informing the patient of the following:

1. What protected health information (PHI) will be collected from patients.
2. Who will have access to that information and why.
3. Who will use or disclose that information.
4. The rights of a research patient to revoke their authorization for use of their PHI.

In order to ensure patient confidentiality, all case report forms and patient information (CT / MRI, if reviewed), fluoroscopic and endoscopic images, ECGs) will be de-identified and replaced with a unique patient identifier. Information will be stored in the office of the local study coordinator, which will be kept in a secure, locked location. The research study coordinators, principal investigator and co-investigators will be the only personnel with access to this data. All data will be stored without any patient information apart from the unique three digit patient identifier. Electronic data will be encrypted and password-protected.

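### Do the outdated ID ranges, and the silence on whether 150 is cumulative, leave the sample on the updated mFAM software undefined?

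*Combined protocol and SAP*

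**What the plan says.** The enrolment ceiling is the same wherever the protocol states it. Section 8 reads "This safety and efficacy study will enroll up to 150 patients across 4 US centers", and the Design row of the Protocol Summary reads "The total enrollment will be up to 150 patients". Section 15 agrees on the sites: "The study will be conducted in up to 4 sites in the United States". The Protocol Summary lists four by name. Section 8 adds that feasibility, not a statistical calculation, set the number, and that the sample is "intended to provide preliminary assessment of safety and performance".

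Section 13.1 sets the numbering for case report forms. The site part reads "Site # must be 2 digits (use leading zero) --- (sites 01-2" and the patient part reads "patient screening/enrollment # (001 – 050". Together they make the full identifier: "Patients will be identified by a 5-digit number and their initials". Section 16, on stored data, mentions no patient information "apart from the unique three digit patient identifier".

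Section 3 explains that the current text is an amendment. It expands an IDE study whose first patients were mapped before four software enhancements were added. The IDE row of Figure 4 shows 50 valid cases. The Objective row of the Protocol Summary and Section 2 both direct the study to the modified software. Section 17 plans descriptive summaries only and does not mention software version.

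**The concern.** Two things look wrong.

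First, the numbering in Section 13.1 does not fit the study described elsewhere. Two of the four sites have no code, and the patient range cannot number 150 people. Section 16 then describes a three-digit identifier where Section 13.1 has five digits plus initials. If patient numbers restart at each site, three digits alone would not be unique across the study.

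Second, the purpose of the amendment is to evaluate the modified software, yet no section says how many patients will be mapped with it. If the 150 includes patients already treated, the sample for the stated objective is smaller than Section 8 suggests. Section 17 expresses categorical variables as a percentage of everyone studied. Read literally, that denominator could mix software versions.

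At stake would be a report whose achieved number cannot be compared with a planned one, and summaries that blur the version under study with its predecessor.

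**Working it through.** No power calculation can be reproduced, because Section 8 says the number was not derived statistically and gives no error rate, effect, standard deviation or margin. The check is counting, followed by a look at how much the ambiguity affects precision.

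**Identifier capacity** (Section 13.1 against Sections 8 and 15)

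| Reading | Numbers available | Against 150 |
|---|---|---|
| As written, study-wide | 50 | 100 short |
| As written, per site | 2 x 50 = 100 | 50 short |
| Four site codes, per site | 4 x 50 = 200 | 50 to spare |

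The site code precedes the patient number, so per-site numbering is the natural reading. On that reading only the site range is out of date. Mean enrolment would be 150 / 4 = 37.5 per site, inside a range of 50. A site that screened more than 50 would run past the printed range, but not past the three-digit field.

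**Five digits against three.** Two site digits plus three patient digits make the five in Section 13.1. Section 16 describes material kept in the local coordinator's office. If numbering is per site, three digits are unique within that store; if it is study-wide, they are unique everywhere. Section 13.2 separately requires a unique subject number together with initials.

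**Ceiling on updated-software patients.** Assumption: the 50 valid IDE cases in Figure 4 are all the earlier patients, and all used earlier software. Figure 4 gives neither a version label nor a number enrolled, so this is illustrative.

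- If 150 counts only new patients: 150.
- If 150 is cumulative: 150 - 50 = 100, or fewer if more than 50 were enrolled earlier.

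**Effect on precision**

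- 95% half-width of a mean in SD units, 1.96 / sqrt(n): 1.96 / sqrt(150) = 0.160 and 1.96 / sqrt(100) = 0.196.
- One-sided 95% upper limit if a given event is never seen, 1 - 0.05^(1/n): 1.98% at n = 150 and 2.95% at n = 100.

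The protocol sets no target half-width and no event-rate threshold, so neither pair of figures straddles a limit the plan has set itself.

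**The case for a change.** The strongest case for a change is that these are current instructions to sites, that correcting them takes a few sentences, and that the question of what 150 counts remains once the numbering is put right. The wording does pull both ways. The Design row speaks of total enrolment, which leans cumulative, while the Enrollment row describes subjects still expected, which leans towards new patients. Section 17 has a single denominator and no split by version.

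The facts in that argument stand: the site range is out of date, the two identifier descriptions differ, and Section 8 does not define the count. The consequences do not follow.

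- A form-numbering convention is not an enrolment limit. Combining it with the earlier cases to get 100 - 50 = 50 updated-software patients would treat a stale label as a cap, which no section supports.
- The objective already names the updated software, and Section 3 places the first patients before the modifications. An analyst following the objective would report the later patients and keep any earlier ones apart. Nothing in the documents proposes pooling.
- Settling the cumulative question would still not fix the analysed number. Patients count as enrolled at consent, some become screen failures, and Section 11 lets operators revert to non-study software. A ceiling is not an achieved sample.
- Difficulty in assigning records to patients is not shown, because the form carries site code, patient number and initials.

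**Conclusion.** The inconsistency is real but needs no change to the design or analysis. The numbering ranges and the three-digit wording are clerical: they restrict nobody's enrolment and alter no estimate, and four site codes alone bring capacity to 200. The undefined count is missing detail rather than an error. The achieved number on the updated software can be reported against either ceiling, 150 or about 100. The difference is 0.16 against 0.20 SD in the half-width of a mean, in a descriptive feasibility study with no hypothesis test in its analysis section and no stated precision target. The 100 rests on the assumption that Figure 4's 50 valid IDE cases are all the earlier patients and used earlier software. The conclusion also assumes that analysts follow the stated objective and keep versions apart. If a report pooled them without saying so, the criticism would belong to that report.
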